## **Introduction**

Chronic obstructive pulmonary disease (COPD) continues to be a significant contributor to morbidity and mortality with significant resources allocated for inpatient COPD exacerbations, defined on clinical symptoms of increased cough from baseline, a change in sputum characteristics from baseline (color, consistency, volume), or increase in the patient's dyspnea from baseline. Current guidelines for treating exacerbations of COPD utilize steroids for reducing inflammation, supplemental oxygen for hypoxemia, antibiotics if suspicion is for a bacterial cause of the exacerbation, and bronchodilators for symptom control and improving airflow per the guidelines published by the Global Initiative for Chronic Obstructive Lung Disease. Additionally, counseling on cessation of cigarette smoking should be given to those still smoking. Supportive therapy with mechanical ventilation (invasive or non-invasive) may be necessary as well as fluid balance management, nutrition, and vaccinations as appropriate for Pneumococcal pneumonia and seasonal influenza. Symptomatic treatment may include pulmonary hygiene with chest physiotherapy such as by a respiratory therapist/percussion vest/Acapella or flutter valve device, and mucolytics such as guaifenesin or N-acetylcysteine (NAC) (as mucolytic or antioxidant).

Although mucolytic therapy is mainly symptomatic and long-term studies are not definitive, some patients may have benefit. Additionally, NAC may have benefit in COPD exacerbations. However, with the recent drug shortages, NAC is not readily available in many hospitals. With difficulty in obtaining a potentially beneficial medication and with significant costs, it is beneficial to explore other possibilities that may deliver equal or better options.

Nebulized hypertonic (3%) saline has been used for sputum induction and as a mucolytic, mainly in pediatric populations with bronchiolitis, and in cystic fibrosis patients with bronchiectasis. Potential benefits of nebulized hypertonic saline include its availability and its costs. Its packaging includes both individual respules for nebulization and bulk solutions.

## Methods

### *Study Population:*

This study will involve 146 patients admitted to Doctors Hospital in Columbus, Ohio from September 2014 through September 2015 with a clinical diagnosis of an acute exacerbation of COPD, defined as an increase in the patient's dyspnea, cough, or change in sputum consistency/volume/color from the patient's baseline during stable conditions. To achieve 80% power to detect a clinically significant difference between study groups, a minimum sample size of 130 patients (65 in each study group) is necessary. To account for issues such as patient study withdrawal and protocol deviations, a sample size of 146 patients (73 per study group) is ideal.

### Inclusion Criteria:

- Patients at least 18 years of age
- Admitted to Doctors Hospital with a clinical diagnosis of COPD within 24 hours.

### Exclusion Criteria:

- Patients younger than 18 years of age
- History of smoking less than twenty pack-years
- Possibility of other primary cause of the patient's change in dyspnea or cough (e.g. pneumonia, congestive heart failure with pulmonary edema, myocardial infarction)
- Patient is found to have a different primary cause after initial enrollment
- Patients admitted over 24 hours prior to contact by study staff/investigator
- Non-English speaking subjects

### *Hypothesis:*

A clinically significant difference exists between albuterol treatments with nebulized 3% saline versus standard saline, for improvements in the patient's modified Borg dyspnea score during an acute exacerbation of COPD.

### *Study Design:*

This randomized, single-blind, prospective study will involve 146 patients admitted to Doctors Hospital with a clinical diagnosis of an acute exacerbation of COPD. Patients will be randomly assigned to 2.5 mg albuterol treatments with either normal saline, as is the standard, or hypertonic saline. The Doctors Hospital biostatistician will create a randomization plan that will be kept with the consent forms. The investigator or study staff will maintain the list and determine the study treatment by subject number.

Once the patient has been identified by the inclusion/exclusion criteria, they will be approached by a study staff member and informed of the opportunity to participate in the study. The study staff will then provide a detailed explanation of the study and obtain patient consent.

Once the patient is enrolled, they will receive the 2.5mg albuterol treatment, and saline solution as determined by the randomization plan (Group 1 will receive 0.9% saline and Group 2 will receive 3% saline), every six hours for at least the first 24 hours, with allowance for PRN (*pro re nata*= as needed) use every four hours by patient request. The nebulized saline will be kept in the pharmacy and will be ordered in the same way as the standard saline. The patient's dyspnea will be evaluated prior to starting the treatment and after the intervention period is completed using the Modified Borg Dyspnea Scale. The scale will be administered by either the investigator or study staff.

Participation in the study will be complete once the patient is discharged from the hospital. All patients will be recommended to have spirometry or full pulmonary function testing as an outpatient once stable, if not already obtained.

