#### *Study Variables:*

The data to be collected from this study will include:

- Demographic (age, sex)
- Treatment group (normal saline/hypertonic saline)
- Modified Borg Scale Score (pre and post treatment)
- prn albuterol use
- 30 day readmission
- 30 day all cause mortality
- Spirometry data within 30 days

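### Study staff both recruit and have access to the randomisation list, and no stated step withholds the next assignment until after consent.

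*Combined protocol and SAP*

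**What the plan says.** The Study Design section of the combined protocol and SAP covers generation, custody and recruitment in consecutive paragraphs.

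- **Generation and storage.** The hospital biostatistician is to "create a randomization plan that will be kept with the consent forms".
- **Custody and use.** "The investigator or study staff will maintain the list and determine the study treatment by subject number".
- **Recruitment.** "Once the patient has been identified by the inclusion/exclusion criteria, they will be approached by a study staff member".
- **Consent.** "The study staff will then provide a detailed explanation of the study and obtain patient consent".
- **Treatment.** After enrolment, the patient receives albuterol with the saline that the plan assigns. The pharmacy stores the saline, which is ordered like the standard product.
- **Baseline score.** The Borg score is taken before treatment starts. The text does not say that it precedes knowledge of the assignment.

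The Exclusion Criteria include a judgement: "Possibility of other primary cause of the patient's change in dyspnea or cough".

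**The concern.** Randomisation protects a comparison only if whoever decides on enrolment cannot know what the next patient will receive. Here the list is available to the same category of staff who recruit, it is stored with the papers used at consent, and it is read by subject number. Someone who foresees the next arm could leave a patient unapproached, or judge that another cause of symptoms is possible, and take the next candidate instead.

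If that happened, the arms could differ in prognosis before any treatment was given, and analysis could not reliably repair it. The patient characteristics listed under Study Variables are age, sex, pre-treatment Borg score and spirometry within 30 days, and the Study Design section only recommends outpatient spirometry. Adjustment removes only the imbalance that these capture. The reviewed text describes no screening log, so patients passed over need leave no trace.

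**Working it through.** **Step 1: look for a safeguard.** The plan gives no figure on this point, so the main check is of the text. Each provision that might conceal the allocation was considered.

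| Provision | Does it conceal the next assignment? |
|---|---|
| Biostatistician creates the plan | No. This covers generation; custody passes to the investigator or study staff |
| Pharmacy stores the saline | No. It is given no allocation or coding role |
| Single-blind design | No. Blinding after assignment does not hide the assignment beforehand |
| Access limits under Data Storage and Confidentiality | No. Access goes to investigators and study staff, the group concerned |
| Treatment follows enrolment | No. This orders the treatment, not knowledge of the list |

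No envelope, central release, independent list holder or reveal-after-consent rule appears in the reviewed text.

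**Step 2: illustrate the possible size.** The inputs are:

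- n = 65 per arm, from Study Population ("a minimum sample size of 130 patients (65 in each study group) is necessary"). No effect size or SD is given, so this figure cannot be reproduced. Solved backwards at 80% power and two-sided 5%, it implies a difference of (1.960 + 0.842) × √(2/65) = 0.49 SD.
- α = 0.05, from Statistical Analysis. A two-sided, two-sample t-test is assumed, because the section states no sidedness and names paired tests.
- No true effect (assumed).
- f and r (both assumed). When the next assignment is one particular arm, staff pass over the top fraction f of candidates on a judgement that correlates r with Borg change. The other arm is unselected.

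The formulas, with φ the standard normal density and z the normal quantile, are:

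- Spurious shift in SD units: d = r × φ(z₁₋f) / (1 − f).
- Noncentrality: d × √(n/2), with √(65/2) = 5.70. The false-positive rate is the two-sided rejection probability of the noncentral t with 128 degrees of freedom.
- Patients passed over per 65 enrolled in the affected arm: 65f/(1 − f).

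The factor φ(z₁₋f)/(1 − f) is 0.1031/0.95 = 0.109 at f = 5%, 0.1755/0.90 = 0.195 at f = 10%, and 0.2800/0.80 = 0.350 at f = 20%.

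| f | Passed over per 65 | r = 0.25: shift, false positives | r = 0.5: shift, false positives |
|---|---|---|---|
| 5% | 3.4 | 0.027 SD, 5.3% | 0.054 SD, 6.1% |
| 10% | 7.2 | 0.049 SD, 5.9% | 0.097 SD, 8.6% |
| 20% | 16.2 | 0.087 SD, 7.9% | 0.175 SD, 16.8% |

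At 73 per arm the rates are 5.3%, 6.0% and 8.2% for r = 0.25, and 6.2%, 9.0% and 18.3% for r = 0.5. A simulation of 40,000 trials per cell at 65 per arm gave 5.3%, 5.7% and 7.9% for r = 0.25, and 6.0%, 8.6% and 17.5% for r = 0.5.

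If both arms were selected in opposite directions at f = 10%, the shift doubles. With r = 0.5 it is 0.195 SD and the rate 19.7%; with r = 0.25 it is 0.097 SD and the rate 8.6%. That case needs about 2 × 7.2 = 14 patients passed over per 130 enrolled.

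**The case against.** The strongest reply is that the text shows an arrangement, not a failure, and that the figures prove little. Much of this stands.

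- A reader might infer that one person holds the list, recruits and consents, or that concealment was broken. The documents support neither. They show overlapping staff categories with nothing to separate them. They also do not say who issues subject numbers or that these follow order of enrolment, so looking up the next assignment is a reasonable inference rather than a stated fact.
- A reader might take 16.8% or 19.7% as estimates. They are not. Both need r = 0.5, a pre-consent impression explaining 25% of the variance in Borg change, and 19.7% also needs opposite selection in both arms. At the low end the effect is negligible.
- The 24-hour criterion, "Patients admitted over 24 hours prior to contact by study staff/investigator", might look like a second opening. It adds little: delay can only make a patient ineligible, and staff who foresaw an assignment could simply not approach.
- Moving the list might be thought sufficient. It is not. The randomisation method is unstated, and staff who learn past assignments could predict later ones if blocks are small and fixed.

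What does not stand is any suggestion that this is merely missing detail. The custody arrangement is stated outright, and following it as written leaves enrolment open to foreknowledge.

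**Conclusion.** The point holds in a limited form. The plan gives list access to a group that also recruits, and no stated step keeps the next assignment from them before consent. The exclusion for another possible primary cause leaves room to act on that knowledge.

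The size of any bias is unknown. With one arm affected, 65 per arm, no true effect and a two-sided two-sample test, the assumed scenarios give shifts of 0.03 to 0.175 SD and false-positive rates of 5.3% to 16.8%. Every f and r is an assumption, so these figures cannot set the seriousness of the point. It rests on the principle that lost concealment is hard to detect or correct afterwards, and that preventing it is a cheap improvement.

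A reader might extend the point to biased Borg scoring or to exclusions after enrolment. The check above models neither, and list custody would cure neither. They are separate points.

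**What to change.** Replace the two sentences on the list in the Study Design section with text such as:

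*The biostatistician will prepare the randomization plan. Staff who screen or consent patients will have no access to it. Each assignment will be revealed only after eligibility is confirmed, consent is signed and the baseline Borg score is recorded.*

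Then name one mechanism:

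1. **Sealed envelopes.** The biostatistician prepares sequentially numbered, sealed, opaque envelopes, opened at the point above. This fits the present arrangement of storage with the consent forms and assignment by subject number. The cost is preparing 146 envelopes.
2. **Held release.** The biostatistician or pharmacy keeps the list and releases each assignment by subject number. The cost is 146 releases, a short wait for each, and out-of-hours cover. The documents do not show that either party can provide this, so it must be confirmed first.

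Under either option, state the randomisation method to the extent that this does not aid prediction. If blocks are used, the biostatistician should vary their sizes and not disclose them to study staff. The change leaves the sample size and treatment unaltered, and it protects allocation up to enrolment only.

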#### *Statistical Analysis:*

We will test the hypothesis that a clinically significant difference in dyspnea scores exists between patients who receive hypertonic saline and those who do not. Descriptive statistics will be produced, using means, medians, ranges and standard deviations for continuous variables, and percentages for categorical variables. Independent variables will include modified Borg scores, 30-day mortality and length of hospital stay. Inferential statistics will determine statistically significant differences between comparison variables, using paired sample t-tests or the Wilcoxon signed rank test. Statistical significance will be evaluated at the 5% ( $\alpha=0.05$ ) level.

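### The trial is called single-blind, but no step masks the saline: an ordinary order has to name the concentration, and the roles that hold the list also administer the Borg scale

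*Combined protocol and SAP*

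**What the plan says.** The Study Design section of the combined protocol and SAP opens: "This randomized, single-blind, prospective study will involve 146 patients". It does not say which party is blinded.

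The two arms differ in saline concentration: "Group 1 will receive 0.9% saline and Group 2 will receive 3% saline". Each accompanies the same albuterol treatment, six-hourly for at least the first 24 hours, with PRN treatments when the patient asks for them.

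Four statements in the protocol bear on masking:

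- **Supply:** "The nebulized saline will be kept in the pharmacy and will be ordered in the same way as the standard saline".
- **List:** the hospital biostatistician creates the randomization plan, which is kept with the consent forms. "The investigator or study staff will maintain the list and determine the study treatment by subject number".
- **Scoring:** the Modified Borg scale is given before treatment and after the intervention period. "The scale will be administered by either the investigator or study staff".
- **Outcome:** the Hypothesis section looks for a difference between arms "for improvements in the patient's modified Borg dyspnea score during an acute exacerbation of COPD".

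PRN albuterol use is a collected variable (Study Variables), and length of stay is listed in the Statistical Analysis section. No section mentions a coded order, a masked or replacement label, matching containers, or a scorer kept unaware of allocation.

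**The concern.** A single blind is a claim that at least one party does not know the arm. Some step has to produce that ignorance, and this plan describes none. The natural reading is that the patient is blinded, because the main outcome is the patient's breathlessness score. The supply rule sends both salines through the ordinary ordering route, and the list is with the people who score the outcome.

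A breathlessness score is subjective. A patient who knows whether they are receiving the new saline or the usual one may rate the change differently for that reason alone. A scorer who knows the arm may influence the answer in how the scale is presented. PRN use starts with the patient's request, so it is open to the same effect. An observed difference between arms could then reflect knowledge of the treatment and not its action, and no analysis of these data could separate the two.

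**Working it through.** **1. What the order must contain.** This follows from setting the Study Design statements side by side.

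- The investigator or study staff hold the list and determine the treatment by subject number.
- The pharmacy stores the saline. It is given no list and no role in allocation.
- The saline is ordered as standard saline is.

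As the plan stands, the pharmacy can learn which product to supply only from the order. The order must therefore state the concentration, and anyone who can read it knows the arm.

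**2. What the container shows.** The plan does not say. If nothing is done to the product, it carries its ordinary label. Relabelling would change that, but none is described. This step is conditional; step 1 is not.

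**3. How often the blind is tested.** Scheduled treatments in the first 24 hours: 24 / 6 = 4 per patient as a minimum. For the planned 146 patients: 146 × 4 = 584 scheduled treatments, plus PRN treatments. At each one the patient's blind depends on nobody showing or mentioning the concentration, and the plan gives staff no instruction on this.

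**4. Who scores.** The list-holders and the Borg administrators are described by the same words: the investigator or study staff. Nothing separates the two tasks, so a failed patient blind is not backed by a blinded scorer.

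**5. Illustration of the stakes.** The documents give no figure for bias, for the Borg SD or for the proportion of patients unmasked, so there is no stated figure to reproduce. The inputs are:

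- n = 65 per arm, the stated minimum, and 73 per arm, the stated ideal (Study Population);
- α = 0.05 (Statistical Analysis), taken as two-sided, which is an assumption;
- a two-sample t-test, also an assumption: the section names paired tests, but the hypothesis compares two independent groups;
- no true effect, and an assumed shift b (in SD) in one arm's mean score caused by knowing the treatment.

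The noncentrality is b × √(n/2) on 2n − 2 degrees of freedom. The false-positive rate is the probability that |t| exceeds its critical value, which is 1.979 for n = 65.

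| Assumed b (SD) | Noncentrality, n = 65 | False positives, n = 65 | False positives, n = 73 |
|---|---|---|---|
| 0 | 0 | 5.0% | 5.0% |
| 0.15 | 0.15 × 5.701 = 0.855 | 13.6% | 14.7% |
| 0.25 | 0.25 × 5.701 = 1.425 | 29.3% | 32.3% |

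A larger sample makes it worse, because a fixed bias is detected more readily. The value of b is the shift in the whole arm's mean. If only half of that arm were unmasked, and the shift fell only on them, b would halve: 0.15 would become 0.075, with a rate of 7.1%.

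**The case against.** **The label is not described.** A reader might infer that every patient sees a labelled concentration at each treatment. The documents do not support that. They say nothing about the content of labels or administration records, or about what is visible at the bedside. The supply sentence concerns storage and the ordering route, and masking that was done but not written down cannot be excluded. This stands, and it is why the container is treated as conditional above. It does not remove the argument about the order, which rests on who holds the list.

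**A patient-only blind allows staff to know.** If the patient is the blinded party, a treating team that can read the order is consistent with the design. A reader might go further and count length of stay as evidence that the blind fails. That would be a criticism of choosing a single blind, not of how this one is carried out, and it is not part of this point. A patient-only blind breaks only if patients see or are told the concentration. The plan does not say that they are, but it contains nothing to prevent it.

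**The error rates are not evidence.** Correct. The arithmetic holds, but the result depends wholly on b, which is assumed. The documents support no particular inflation of the false-positive rate.

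**Masking the supply alone would not be enough.** Also correct. A code by subject number hides nothing from a scorer who holds the list by subject number, and a pharmacy without the list cannot dispense against a code. The fix has to move the list as well.

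**Conclusion.** The concern holds in a limited form. The protocol claims a single blind, names no blinded party and describes no step that produces one. Given who holds the list, an ordinary order has to reveal the arm; unless the product is relabelled, so does the container. The same roles hold the list and administer the subjective outcome on which the hypothesis rests.

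The conclusion is that the blind cannot be relied on from what is written, not that it has been shown to fail. It assumes that the Study Design text is complete about who has the list. The size of any bias is unknown: 14% to 29% false positives at 65 per arm shows what 0.15 to 0.25 SD would do and is not an estimate for this trial. The stated sample sizes are not in question here. The change should be made, because a coded supply is a better method than the one described and not merely a missing detail to be filled in.

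**What to change.** Revise the Study Design section as follows.

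1. The pharmacy holds the randomization list. Orders for both arms use one entry: 'study saline, subject number __'.
2. The pharmacy dispenses both concentrations in the same type of container, with a coded label that does not show the concentration. Immediate unmasking is available when patient care needs it.
3. The person administering the Borg scale neither holds nor sees the list.
4. The protocol names the patient and the Borg administrator as the blinded parties. It adds that taste may still unmask some patients, so the Borg result is not described as fully blinded.

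**Cost.** The pharmacy must relabel or draw up at least 4 scheduled doses per patient, which is at least 584 for 146 patients, plus PRN doses. The Introduction says of hypertonic saline that "Its packaging includes both individual respules for nebulization and bulk solutions", so drawing up is plausible, but that is a general statement and does not show what this pharmacy stocks. The pharmacy also takes over the list, and scoring has to be assigned to someone without access to it. No additional patients are needed, and no dose or schedule changes.

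### The roles that hold the allocation list also obtain the Modified Borg score, and nothing keeps whoever takes the post-treatment score unaware of the arm

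*Combined protocol and SAP*

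**What the plan says.** All references are to the combined protocol and SAP.

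- **Blinding.** Study Design opens: "This randomized, single-blind, prospective study will involve 146 patients". Neither that section nor any other says which party is blinded.
- **The list.** Study Design states: "The Doctors Hospital biostatistician will create a randomization plan that will be kept with the consent forms". It continues: "The investigator or study staff will maintain the list and determine the study treatment by subject number". The same section has study staff obtain consent.
- **The outcome.** Study Design sets two assessments: "The patient's dyspnea will be evaluated prior to starting the treatment and after the intervention period is completed using the Modified Borg Dyspnea Scale". On who carries them out, it says: "The scale will be administered by either the investigator or study staff".
- **The role of the score.** The Hypothesis section compares the two salines "for improvements in the patient's modified Borg dyspnea score during an acute exacerbation of COPD". In Study Variables, the pre- and post-treatment Borg score is the only dyspnea measure.

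The plan does not describe a masked assessor, a division between looking up treatment and scoring, a limit on who may see the list, or a scripted or self-completed form of the scale. It also does not say whether the baseline score comes before or after the look-up.

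**The concern.** A dyspnea rating is subjective. Someone who knows the arm can influence it without intending to, through how the question is introduced, whether an answer is probed, or how an in-between answer is written down. A shift that enters at the post-treatment score passes directly into the change from baseline, so the pre-treatment score gives no protection.

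If this happened differently in the two arms, it could not be told apart from an effect of the saline. A larger sample or a different test would not remove it. The other outcomes that the plan collects, such as 30-day mortality and readmission, are less exposed but do not test the dyspnea hypothesis.

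This is separate from concealing the allocation before enrolment. The bias enters after treatment and would remain even if the allocation were perfectly concealed at consent.

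**Working it through.** **Step 1: who does what, from Study Design.**

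| Task | Assigned to |
|---|---|
| Create the randomization plan | Hospital biostatistician |
| Store the plan | With the consent forms |
| Obtain consent | Study staff |
| Maintain the list and determine treatment | Investigator or study staff |
| Administer the Borg scale, before and after | Investigator or study staff |

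The last two rows name the same roles, and no sentence separates the people who fill them. A site that followed the plan to the letter could have one person look up the arm and later obtain the score. It could equally use two people. The plan allows either.

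**Step 2: what the blinding label settles.** If it means that only the patient is blinded, unmasked elicitation is allowed. If it means that the assessor is blinded, the plan gives no procedure for achieving this, and its division of tasks works against it.

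**Step 3: sensitivity of the comparison.** The section on study population gives 65 per group for 80% power, and 73 per group after allowing for withdrawals and deviations. Statistical Analysis gives a 5% significance level. The plan states no effect size, SD or sidedness, so its sample size cannot be reproduced from its own inputs. I therefore assume a two-sided, between-arm two-sample t-test and work in SD units. The section names paired tests, so the between-arm test is my assumption.

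Standard error of the difference at 65 per arm: √(2/65) = 0.1754 SD.

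Difference detectable with 80% power: (1.960 + 0.842) × 0.1754 = 0.491 SD by the normal approximation, or 0.495 SD by the t-test.

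Now suppose that there is no true effect and that elicitation shifts the between-arm difference by b SD. With δ = b / √(2/n), the probability of a significant result is

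P(reject) = P(T > t*) + P(T < −t*),

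where T is noncentral t with 2n − 2 degrees of freedom and noncentrality δ. At n = 65 there are 128 degrees of freedom and t* = 1.979.

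| Assumed shift b | δ at 65 per arm | P(reject), 65 per arm | P(reject), 73 per arm |
|---|---|---|---|
| 0 | 0 | 5.0% | 5.0% |
| 0.10 SD | 0.10/0.1754 = 0.570 | 8.7% | 9.2% |
| 0.20 SD | 0.20/0.1754 = 1.140 | 20.5% | 22.5% |
| 0.25 SD | 0.25/0.1754 = 1.425 | 29.3% | 32.3% |

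The normal approximation at 65 per arm gives 8.8%, 20.7% and 29.7%. The rates are higher at 73 per arm because a fixed bias becomes larger relative to a smaller standard error.

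**The case against.** The case on the other side has real substance.

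- **The score is the patient's own rating.** If the patient is blinded, the person producing the number does not know the arm. Influence through elicitation and recording is a weaker route than scoring by an unmasked observer. This stands and limits how serious the point is.
- **The mode is not stated.** A reader might infer that the Borg is a spoken, prompted interview. The plan says only that it is administered, which also covers handing over a printed scale. The spoken reading is unsupported, but nothing in the plan requires self-completion either.
- **Roles are not individuals.** A reader might infer that one person both looks up the arm and takes the score. The text names shared roles only. The gap is that nothing keeps the tasks apart.
- **There is no contradiction.** A reader might infer that unmasked staff breach the declared blinding. Staff who know the arm are compatible with a single-blind design. What can be shown is that the blinded party is not named.
- **The direction is not fixed.** The hypothesis is of a difference, without a stated direction. That staff would favour 3% saline is plausible from the Introduction, but it is inference.
- **The figures are generic.** They would apply to any trial with 65 per arm. This is correct: they show sensitivity, not likely harm.

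None of these points supplies a safeguard. The plan as written still allows its key outcome to be obtained by someone who knows the arm.

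**Conclusion.** The point holds as a gap in the protection of the main outcome. The plan gives the list, the look-up and the Borg assessment to the same roles, does not require the post-treatment score to be obtained without knowledge of the arm, and does not say who is blinded.

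The size of any resulting bias is unknown. The rise from 5% to about 9% to 29% rests on assumed shifts of 0.10 to 0.25 SD, no true effect, 65 per arm, and a two-sided between-arm t-test. The documents support none of the shift sizes.

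The documents do not support the stronger conclusion that the Borg comparison is biased, or that the trial breaches its own blinding. The change should be made before data collection, because a score influenced at elicitation cannot be repaired in the analysis. It is a worthwhile, inexpensive improvement rather than a flaw that by itself invalidates the trial.

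**What to change.** Amend Study Design as follows.

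1. State that the patient is blinded, and that the post-treatment Borg score is obtained without knowledge of the arm.
2. Have the patient mark a printed scale, introduced with fixed scripted wording and labelled with the subject number only.
3. Have the sheet handed over by an existing study staff member who has seen neither that subject's allocation nor the treatment order. If the patient cannot mark the sheet, the same person reads the scale aloud. Barring only the person who looked up the treatment would not be enough, since others could learn the arm from the list or the order.
4. Keep the allocation list apart from the consent forms, with access limited to whoever looks up and orders the treatment.
5. Take the baseline Borg score before the allocation is looked up.

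The cost is a wording change, a printed form, a short script and a division of tasks among existing staff. The downside is minor scheduling inconvenience. The sample size and the study treatments do not change.
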